4.1. Primary Endpoint

- Frequency of treatment-emergent adverse events (TEAEs), drug-related adverse events (AEs), discontinuations due to AEs and deaths.

4.2. Secondary Endpoints

- Global Response as measured by:
 - Percentage of subjects with Complete Response or Partial Response at EoT (key secondary endpoint), Day 42 and Day 84, as determined by the DRC
 - Percentage of subjects with Complete Response or Partial Response at EoT, Day 42 and Day 84, as determined by the Principal Investigator
- Overall survival, defined as the time from randomization to time of death up to Day 84
- Percentage of subjects who died (any cause) at Days 42 and 84
- Absolute reduction and percent change in serum GMI from Baseline to Weeks 1, 2, 4 and 6
- Percentage of subjects with the following changes in serum GMI from Baseline:
 - Fifty percent reduction or greater at Weeks 1, 2, 4 and 6
 - Twenty-five percent reduction or greater at Weeks 1, 2, 4 and 6
 - Any percent reduction at Weeks 1, 2, 4 and 6
 - Reduction equal to or greater than 0.25 at Weeks 1, 2, 4 and 6
 - Reduction to <0.5 at Weeks 1, 2, 4 and 6
- Time to achieve the following changes in serum GMI from Baseline:
 - Fifty percent reduction
 - Twenty-five percent reduction
 - Any percent reduction
 - Reduction equal to or greater than 0.25
 - Reduction to <0.5 in 2 consecutive samples
- Percentage of subjects with:
 - Clinical Response at EoT, Day 42 and Day 84, as determined by the DRC
 - Mycological Response at EoT, Day 42 and Day 84, as determined by the DRC
 - Radiological Response at EoT, Day 42 and Day 84, as determined by the DRC

- Percentage of subjects with:
 - Clinical Response at EoT, Day 42 and Day 84, as determined by the Principal Investigator
 - Mycological Response at EoT, Day 42 and Day 84, as determined by the Principal Investigator
 - Radiological Response at EoT, Day 42 and Day 84, as determined by the Principal Investigator
- Ibrexafungerp and voriconazole plasma concentrations population PK analysis.

4.3. Exploratory Endpoints

- Absolute and percentage changes in serum β -D-glucan from Baseline at Weeks 1, 2, 4 and 6
- Percentage of subjects with the following changes in serum β -D-glucan from Baseline (if positive):
 - Fifty percent reduction or greater at Weeks 1, 2, 4 and 6
 - Twenty-five percent reduction or greater at Weeks 1, 2, 4 and 6
 - Any percent reduction at Weeks 1, 2, 4 and 6
 - Negative serum β -D-glucan at Weeks 1, 2, 4 and 6
- Percentage of subjects that convert from positive plasma *Aspergillus* PCR at Baseline to negative at Weeks 1, 2, 4 and 6
- Absolute change in Karnofsky score from Baseline to Days 42 and 84
- Time to achieve a 10-point improvement in Karnofsky score from Baseline
- Percentage of subjects with a recurrence of the baseline fungal infection within 42 days (Week 6) after EoT
- Relationship between GMI decrease and ACM at Days 42 and 84
- Relationship between GMI decrease and Global response at Day 42 and EOT
- Relationship between GMI decrease and Clinical response at Day 42 and EOT
- Relationship between GMI decrease and Radiological response at Day 42 and EOT
- Number of subjects with complete response and alive at Days 42 and 84
- Days of hospital stay and Days of ICU stay
- Percentage of subjects who are able to receive on-schedule administration of the planned therapies for their underlying condition.

5. Analysis Populations

5.1. Screened Population

The Screened Population will include all subjects screened. Unless specified otherwise, this set will be used for subject listings and for summaries of subject disposition. The summary of subject disposition will be according to randomized treatment.

5.2. Intent-to-Treat (ITT) Population

The ITT Population will include all randomized subject who receive at least one dose of randomized study medication. This population will be the primary population for the analysis of efficacy data. Analysis will be according to randomized treatment.

5.3. Safety Population

The Safety Population will include all randomized subject who receive at least one dose of randomized study medication. This population will be the primary population for the analysis of safety data. Analysis will be according to actual treatment received.

5.4. Modified Intent-to-Treat (MITT) Population

The MITT Population will be a subset of the ITT Population that will include subjects who have a probable or proven IPA at baseline, per DRC, with at least one positive serum GMI at baseline. Analysis will be according to randomized treatment.

5.5. Per-Protocol (PP) Population

The PP Population will be a subset of the ITT Population and will include subjects who have a probable or proven IPA at baseline, per DRC, with at least one positive serum GMI at baseline, have completed at least 14 days of randomized study treatment and have at least one efficacy assessment post baseline (Treatment Day 1) and no major protocol deviations. Analysis will be according to randomized treatment.

5.6. Pharmacokinetic Population

The PK Population will include all enrolled subjects who provide at least one PK sample. The PK Population is the primary population for the analysis of PK data. Analysis will be according to actual treatment received.

6. General Aspects for Statistical Analysis

6.1. General Methods

- Unless otherwise specified, summaries will be presented for each treatment group.
- Continuous variables will be summarized using the number of observations (n), mean, standard deviation (SD), median, minimum, and maximum. Categorical variables will be summarized using number of observations (n), frequency and percentages of subjects.
- All relevant subject data will be included in listings. All subjects entered into the database will be included in subject data listings.
- All data will be summarized at the nominal time point at which they were collected. Repeat and unscheduled assessments will not be used in the data summaries, however these will be listed.

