15.17 Safety Laboratory Tests

Safety laboratory tests (hematology, blood chemistry and urinalysis) will be performed at Screening and Baseline (Treatment Day 1), and on Treatment Days 7 and 14, at EoT and 6-Week FU. Electrolyte disturbances such as hypokalaemia, hypomagnesaemia and hypocalcaemia should be monitored and corrected, if necessary, prior to initiation and during voriconazole therapy. If clinically indicated, safety tests will be repeated every 14 days following Treatment Day 14 up to EoT, and at unscheduled visits. These may also be done more frequently as followup to a laboratory abnormality. If the subject is still receiving study drug by Day 42 (i.e., EoT has not occurred), a safety lab assessment should be conducted on Day 42 or on Day 56. Safety laboratory tests will be processed at a central laboratory. Procedures for collecting, storing, and shipping samples to the central laboratory are described in the study laboratory manual.
SCYNEXIS, Inc.	IND #107,521
PROTOCOL SCY-078-206	Version 5.0

Results from safety laboratory test by the central lab will be made available to the sites on an ongoing basis; however, the site should not relay on timely availability of these result to make medical decisions for subjects' care.

Additional laboratory tests should be collected and analyzed by the local laboratory, as needed, to make real-time medical decisions. Specifically, in line with voriconazole label

recommendations, serum transaminase levels, bilirubin levels, serum electrolytes (potassium, magnesium and calcium) and amylase and lipase should be monitored at initiation of voriconazole therapy (Day 1) and then weekly during the first month of treatment (Day 7, Day 14, Day 21 and Day 28). Monitoring frequency of these laboratory parameters may be reduced to monthly intervals during continued use of voriconazole if no clinically significant changes are noted.

The following laboratory parameters will be determined for all samples sent to the central laboratory:

Hematology

• White blood cell (WBC) count

Red blood cell (RBC) count

 Hemoglobin Hematocrit

- Platelet count
- Differential WBC count will include percentages for segmented neutrophils, lymphocytes, monocytes, eosinophils and basophils, and absolute counts for neutrophils, lymphocytes, atypical lymphocytes, monocytes, eosinophils and basophils.

Blood Chemistry

- Sodium
- Potassium
- Magnesium
- Calcium
- Alkaline Phosphatase
- Chloride
- Blood urea nitrogen (BUN)
- Creatinine

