17.3 Events of Clinical Interest

The following are considered events of clinical interest (ECIs), and must be recorded as such on the AE eCRF when the PI becomes aware of the ECI:

- QTc >500 ms or a >60-ms change from Baseline, confirmed by repeat testing
- ALT or AST >8 x ULN, if new compared to Baseline, confirmed by repeat testing
- ALT or AST >5 x ULN for more than 2 weeks and if new compared to Baseline, confirmed by repeat testing
- ALT or AST >3 x ULN and either total bilirubin >2 x ULN or INR >1.5 and if new compared to Baseline, confirmed by repeat testing
- ALT or AST >3 x ULN, confirmed by repeat testing, with the appearance of fatigue, nausea, vomiting, right upper quadrant pain or tenderness, fever, rash, and/or eosinophilia (>5%)]

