10.4. Laboratory Evaluations

Blood samples are taken at Screening, Day 1, Day 7, Day 10, Day 14, then every 14 days as required, up to EoT and Follow-Up for the central evaluation of hematology, chemistry and urinalysis laboratory tests.

Summaries of laboratory data will be based on the Safety Population.

Continuous laboratory results for hematology, chemistry and urinalysis will be summarized, by treatment, at baseline, Day 7, Day 10, Day 14, and all further scheduled visits, up until EoT and Follow-Up. In addition, for post baseline visits, a summary will also be given for the change from baseline.

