10.5. Vital Signs

Vital signs include SBP, DBP, pulse rate, respiratory rate and body temperature, and are collected at Screening, Day 1 and EoT.

Temperatures captured in °F will be converted to °C using the formula:

$$\text{Temperature (in } ^\circ\text{C)} = 5/9 (\text{Temperature [in } ^\circ\text{F]} - 32).>$$

Vital signs will be summarized, by treatment, for the Safety Population at baseline and EoT. In addition, at EoT a summary will be given for the change from baseline.

10.6. 12-Lead ECG

A 12-lead ECG is collected at Screening, Day 1, Day 10 and EoT.

Summaries of ECG data will be based on the Safety Population.

Overall interpretation will be summarized, by treatment, at baseline, Day 10 and EoT.

ECG parameters, including heart rate, PR interval, RR interval, QRS interval and QTcF interval will be summarized, by treatment, at baseline, Day 10 and EoT. In addition, at Day 10 and EoT a summary will be given for the change from baseline.

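### Peak liver-test or QTcF values found only at repeat or unscheduled assessments enter no by-arm laboratory or ECG table, and the SAP drops the ECI and shift summaries that the protocol promises

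*SAP*

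**What the plan says.** SAP 6.1 has all data summarised at nominal time points and adds: "Repeat and unscheduled assessments will not be used in the data summaries, however these will be listed". The statistics for continuous variables are also set there: "Continuous variables will be summarized using the number of observations (n), mean, standard deviation (SD), median, minimum, and maximum".

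For laboratory data, SAP 10.4 describes central evaluation, and continuous results "will be summarized, by treatment, at baseline, Day 7, Day 10, Day 14, and all further scheduled visits", with changes from baseline. For ECG, SAP 10.6 says that the "QTcF interval will be summarized, by treatment, at baseline, Day 10 and EoT", so there are two post-baseline points. Neither section has a table of worst post-baseline value, of threshold categories or of shifts.

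The protocol relies on extra testing for the values of most interest. Section 15.17 says of safety laboratory tests: "These may also be done more frequently as followup to a laboratory abnormality". Section 15.8 provides for ECGs at unscheduled visits. All five ECI definitions in section 17.3 require repeat testing, for example "ALT or AST >8 x ULN, if new compared to Baseline, confirmed by repeat testing" and "QTc >500 ms or a >60-ms change from Baseline, confirmed by repeat testing". Protocol 19.6.2 commits to summarising ECIs and shifts against the laboratory reference range. SAP section 10 includes neither, and SAP 12 says that nothing departs from the protocol's planned analyses.

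**The concern.** Safety is the primary objective. Protocol 8.1 reports transient liver-test increases with SCY-078, and protocol 15.17 sets liver monitoring in line with the voriconazole label. A short-lived high ALT or QTcF value is what a reader would want counted by arm.

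By-visit summaries at scheduled visits can look alike in the two arms while such values sit only in listings. Listings give the values subject by subject but no count by arm. The ECI and shift summaries promised in the protocol would have gone some way to fill that gap, and they are missing from the SAP without being declared.

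**Working it through.** The documents give no figure on this point, so there is nothing to reproduce. The check is mainly textual.

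**Where a peak value can be displayed**

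| How the value arises | By-visit lab/ECG table | By-arm TEAE table | Listing |
|---|---|---|---|
| Scheduled central lab or scheduled ECG | Yes, including through the maximum (SAP 6.1) | If recorded as an AE or ECI | Yes |
| Repeat or unscheduled | No (SAP 6.1) | If recorded as an AE or ECI, as an event without its value | Yes |
| Local laboratory | No (SAP 10.4 covers central evaluation) | If recorded as an AE or ECI | Only if in the eCRF |

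The third row has a different cause from the second. Loss of local results comes from 10.4, not from 6.1.

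**What the TEAE route carries.** ECIs must be identified on the AE eCRF (protocol 17.3). Clinically significant laboratory abnormalities (17.1) and clinically relevant ECG abnormalities (15.8) are AEs, and AEs are collected at unscheduled visits (15.29). SAP 10.3 tabulates TEAEs by arm, by SOC and PT and by maximum severity. It has no ECI grouping. Apart from ECIs, entry depends on the investigator's judgement. Severity is graded by effect on daily activities (protocol 17.7), so a symptom-free high ALT can be graded mild.

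**Illustration 1: how sparse the central laboratory schedule is.** Assumptions, not from the documents: treatment to Day 70; one elevation lasting D days, with onset uniform over Days 15 to 69 (55 days). If the only summarised samples after Day 14 are on Day 42 and at EoT on Day 70, then D onsets cover Day 42 and D − 1 cover Day 70. If all 14-day labs are done, Days 28 and 56 are added.

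| D (days) | Day 42 and EoT only: seen | Missed | All 14-day labs: seen | Missed |
|---|---|---|---|---|
| 5 | (5 + 4)/55 = 16% | 84% | (5 + 5 + 5 + 4)/55 = 35% | 65% |
| 10 | (10 + 9)/55 = 35% | 65% | (10 + 10 + 10 + 9)/55 = 71% | 29% |
| 20 | (20 + 19)/55 = 71% | 29% | 55/55 = 100% | 0% |

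**Illustration 2: whole treatment period.** Assumptions: onset uniform from Day 2 to last treatment day T, EoT on Day T. The chance that at least one summarised visit falls within the elevation is the number of onset days s for which some visit v satisfies s ≤ v ≤ s + D − 1, divided by T − 1. For ECG with T = 91 and D = 7, onsets on Days 4–10 cover Day 10 and onsets on Days 85–91 cover EoT: (7 + 7)/90 = 0.16.

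| Summarised visits | T = 42; D = 3 / 7 / 14 | T = 91; D = 3 / 7 / 14 |
|---|---|---|
| Labs: Days 7, 14, EoT, plus Day 42 or 56 if T > 42 | 0.22 / 0.49 / 0.66 | 0.13 / 0.30 / 0.46 |
| Labs: also Day 10 and every 14-day visit | 0.37 / 0.66 / 1.00 | 0.30 / 0.61 / 1.00 |
| ECG: Day 10 and EoT | 0.15 / 0.34 / 0.56 | 0.07 / 0.16 / 0.26 |

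Both tables describe how much of the treatment period scheduled sampling covers. Neither estimates what 6.1 removes: that also needs the chance that a repeat or unscheduled sample was taken, which the documents do not give.

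**Weight of one subject.** SAP 3.4 gives about 11 per group: 1/11 = 9.1%.

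**The case against.** Keeping unscheduled values out of by-visit tables is an ordinary convention, and the 6.1 sentence directly follows the nominal-time-point rule. It need not be read as reaching everything: SAP 6.2 defines baseline as the last non-missing pre-dose value without excluding unscheduled results. With 22 subjects, the listed values can also be read by hand. All of this is fair. It argues for keeping the convention in by-visit tables, but it does not supply a by-arm count.

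Four stronger readings are tempting, and the documents do not support them.

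- That these findings never reach any by-arm safety table. They can reach the TEAE tables by the route set out in the working.
- That peaks are mostly found at repeat or unscheduled visits. No document says so. Repeat confirmation presupposes a first abnormal value; if that came from a scheduled central sample or a scheduled ECG, it stays in the by-visit table.
- That 84%, 65% and 29% measure the loss due to 6.1. They describe sparse central sampling under one unfavourable schedule, and fall to 65%, 29% and 0% if all 14-day labs are done. They also leave out the period up to Day 14, where sampling is densest, and say nothing about QTc.
- That the primary endpoint is damaged. It is the frequency of TEAEs, drug-related AEs, discontinuations due to AEs and deaths, and 6.1 does not remove AEs from it.

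**Conclusion.** The point holds as a gap in display. Under SAP 6.1 with 10.4 and 10.6, a peak ALT, AST, bilirubin or QTcF value found only at a repeat or unscheduled assessment is absent from the by-arm laboratory and ECG tables. The TEAE tables fill the gap only in part. Separately, and needing no assumption, the ECI and shift summaries in protocol 19.6.2 are missing from the SAP while SAP 12 declares no deviations.

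The number of values affected cannot be derived from the documents. The illustrations show only that short elevations, and most ECG changes, could fall between summarised visits, whereas a 14-day laboratory elevation would not if Day 10 and every 14-day visit were sampled. This is a worthwhile, low-cost improvement to the reporting of a safety-primary trial and does not invalidate the primary endpoint.

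**What to change.** 1. In SAP 6.1, limit the exclusion of repeat and unscheduled assessments to by-visit tables.
2. In SAP 10.4 and 10.6, add by-arm tables of each subject's worst post-baseline ALT, AST, total bilirubin, QTcF and QTcF change. Use all scheduled, repeat and unscheduled results in the database, and give counts above the protocol 17.3 cut-offs.
3. Include local results only where they are in the eCRF, scaled to their own reference range. Protocol 15.17 does not say that local safety results are entered there, unlike local GMI (15.15), β-D-glucan and PCR (15.16) and voriconazole levels (15.18).
4. Restore the ECI and shift summaries on the same basis. The ECI record on the AE eCRF can supply the parts of 17.3 that a worst-value table cannot, such as duration, symptoms and INR, which is not in the central panel listed in 15.17. If either summary is dropped on purpose, say so in SAP 12.

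The cost is a few extra tables and the handling of local reference ranges. No new data are needed, and SAP 3.7 places unblinding after database lock, so the tables can be specified before then. The drawback is that a worst value depends partly on how often a subject is tested. Showing the number of post-baseline results per subject by arm would let a reader judge this.

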6.2. Key Definitions

Study Day 1 is defined as the day of the first dose of study medication. Study Day -1 is defined as the day before the day of the first dose of study medication.

For days on or after the day of the first dose of study medication, Study Day will be calculated as:

$$\text{Study Day} = \text{Assessment Date} - \text{Date of First Dose of Study Drug} + 1.$$

For days before the day of the first dose of study medication, Study Day will be calculated as:

$$\text{Study Day} = \text{Assessment Date} - \text{Date of First Dose of Study Drug}.$$

Baseline is defined as the last non-missing assessment prior to the first dose of study drug.

Change from baseline is defined as:

$$\text{Post-Baseline Value} - \text{Baseline Value}.$$

6.3. Missing Data

Data from subjects who withdraw will be included, where possible, in all summaries and analyses.

For the efficacy analyses, subjects who do not have an EoT assessment will be assigned an indeterminate outcome, so will be classed as treatment failures for the corresponding efficacy analyses. For subjects who withdraw from the study early, every effort will be made to collect EoT visit information at the point of withdrawal.

6.4. Visit Windows

All data will be summarized at the nominal time point at which they were collected. Visit windows will not be used.

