15.8 Twelve-Lead Electrocardiogram

A 12-lead ECG will be obtained and evaluated locally by a physician for the presence of abnormalities at Screening and Baseline (Treatment Day 1), once between days 7 and 21, at EoT and at unscheduled visits, if applicable.

Heart rate, PR interval, QRS, QT and QTcF values will be recorded in the eCRF. Any clinically relevant abnormality will be recorded as AE accordingly and will be followed up to resolution/satisfaction.

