- q. Blood samples for voriconazole level determination will be performed for all study subjects at a central laboratory. For the first 20 randomized subjects, blood PK samples will be collected predose on Treatment Days 1, 3, 7 and 14, approximately within 1 hour before dosing and at 2-4 hours and 6-8 hours after dosing on Treatment Days 1, 7 and 14. The PK data from the first 20 subjects will be assessed in an interim PK analysis. For subjects subsequently randomized, blood PK samples will be collected predose on Treatment Days 1, 3, 7 and 14, approximately within 1 hour before dosing, and on Treatment Days 1, 7 and 14 at 4-8 hours after dosing. The time of dosing and sample collection must be recorded in the eCRF.
- r. Blood samples for voriconazole level determination to be collected as needed (e.g., within 7 days after making any dose adjustment or evidence of toxicity) and sent to the central lab.
- s. Samples for ibrexafungerp PK will be collected predose on Treatment Days 1, 3, 7 and 14, approximately within 1 hour before dosing, and at 2-4 hours and 6-8 hours after dosing on Treatment Days 1, 7 and 14.. The time of dosing and sample collection must be recorded in the eCRF and on the subject’s medical record.
- t. All randomized subjects will receive either ibrexafungerp + voriconazole or ibrexafungerp placebo + voriconazole.
- u. For non-hospitalized patients only.

Table 2 Schedule of Treatment Visits and Procedures for Days 42 and 84 (Study SCY-078-206)

PROCEDURE	Visit/contact	Visit/contact
Visit	Survival	Survival
	Day 42	Day 84
Days (allowable window)	± 2	± 4
Assessment of treatment outcome	X	X
Subject Status (alive/ deceased)	X	X
Karnofsky Score	X	X

4. Endpoints

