8.2.4. GMI Reduction

GMI is assessed at screening, Day 1, Day 3, Day 5, Day 7, Day 10, Day 14, then every 14 days during treatment, at EoT and at Follow-up.

GMI reduction at a visit will be calculated as the baseline result minus the result at the visit.

GM reduction will be summarized, by treatment, for the Intent-to-Treat Population at Week 1 (Day 7), Week 2 (Day 14), Week 4 (Day 28) and Week 6 (Day 42).

In addition, percentage reduction will also be summarized.

Note, assessment of GMI endpoints will be based on the central laboratory results. Local results will be listed only.

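### Samples labelled EoT have no route into the Week 4 and Week 6 biomarker summaries, even when drawn on time for those weeks

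*SAP*

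**What the plan says.** SAP 6.4 has two sentences: "All data will be summarized at the nominal time point at which they were collected", and "Visit windows will not be used". SAP 6.1 repeats the label rule and adds: "Repeat and unscheduled assessments will not be used in the data summaries, however these will be listed".

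SAP 8.2.4 gives the GMI sampling days up to Day 14, "then every 14 days during treatment, at EoT and at Follow-up". It summarises reductions at Weeks 1, 2, 4 and 6, equated to Days 7, 14, 28 and 42. SAP 8.2.9 and SAP Table 1 put beta-D-glucan on the same schedule, and Table 1 does the same for PCR.

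The separate Day 42 and Day 84 contacts (SAP Table 2, Protocol Table 5) list three items: treatment outcome, vital status and Karnofsky score. Protocol 15.23 allows the survival determination at these contacts to be made by phone.

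Protocol 13.1.2 recommends at least 6 weeks of treatment and caps it at 13. It ties duration to clinical improvement, immunosuppression and imaging response. SAP 13.2.5.2 makes the default percentage denominator those subjects in the analysis set who have an observation.

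**The concern.** At Weeks 4 and 6 the only scheduled biomarker sample that clearly carries the week's label is an on-treatment one. Treatment can also end on exactly those days, and 6 weeks is the recommended minimum. A sample from such a subject is collected and assayed at the right time, yet under a strict reading of the label rule it counts towards EoT and towards no week.

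Whether a subject is still on treatment at Day 28 or Day 42 is settled after randomisation and depends on how the subject is doing. Some stop because they have improved, and Protocol 12.3 lets others stop for lack of efficacy. Summaries limited to those still on treatment compare subsets that may differ between arms. GMI at these weeks is a named secondary endpoint, and Protocol 19.1 gives preliminary effect-size estimates as the study's main goal.

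**Working it through.** The plan states no figure to reproduce, so the check is the visit calendar followed by the path of one sample.

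**Inputs.** 14-day visits have a ±2-day window and EoT a ±1-day window (Protocol Table 4, SAP Table 1). Recommended minimum treatment is 6 weeks (Protocol 13.1.2). Study Day 1 is the first dose (SAP 6.2). About 22 subjects are randomised, 11 per arm (SAP 3.4).

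**Calendar.** Visits from Day 14 fall on 14 + 14k, that is Days 14, 28, 42, 56, 70 and 84. Week 4 (k = 1) and Week 6 (k = 2) are both on-treatment visits.

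**Overlap.**
- Six weeks of dosing ends on Day 1 + 42 − 1 = Day 42. The EoT window is Days 41–43, inside the Day 42 visit window of Days 40–44.
- If EoT is instead counted from the day after the last dose, it is 43 ± 1 = Days 42–44, still inside.
- For a stop on Day 28, the EoT window is Days 27–29, inside Days 26–30.

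So an EoT sample at either point meets the timing that the protocol sets for the weekly visit.

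**Path of that sample.**
1. Recorded as EoT, it is summarised under EoT (SAP 6.4).
2. The GMI and beta-D-glucan change summaries show Weeks 1, 2, 4 and 6 only (SAP 8.2.4, 8.2.9), so it enters no row.
3. The target-reduction percentages in SAP 8.2.5, 8.2.10 and 8.2.11 state no other denominator, so SAP 13.2.5.2 applies and the subject leaves the denominator as well as the numerator.
4. SAP 6.3 does not restore it. Its failure rule covers subjects without an EoT assessment, and its general wish to include withdrawn subjects' data gives no mapping.

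**Not affected.** Time to target (SAP 8.2.6) uses the date of achievement. The GMI/mortality boxplots (SAP 8.2.15) use the last available decrease up to Day 42 or Day 84. The same report could thus hold two Day 42 GMI displays based on different subjects.

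**Sensitivity.** One subject is 1/11 = 9.1% of an arm, or more where the baseline condition reduces the denominator. If m of 11 subjects have their sample labelled EoT, and the target rates are p_on among the rest and p_off among those m, the reported rate differs from the all-subject rate by (m/11) × (p_on − p_off). Purely for illustration, assume p_on = 80% and p_off from 30% to 80%:
- m = 2: all-subject rate from (9 × 0.8 + 2 × 0.3)/11 = 71% to 80%, against 80% reported.
- m = 4: all-subject rate from (7 × 0.8 + 4 × 0.3)/11 = 62% to 80%, against 80% reported.

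The documents give neither m nor these rates.

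**The case against.** **The Day 42 visit may take GMI.** Protocol 15.15 opens by calling for serum GMI at every study visit. Protocol 15.21 lists it among the procedures for assessing treatment outcome, and Table 5 requires that assessment at Day 42. This has weight. Against it, 15.15 goes on to name treatment visits, EoT, 6-Week FU and unscheduled visits, the Day 42 table has no GMI row, and the contact may be by phone. The text is ambiguous and should be reconciled. A reader might infer that Week 6 GMI is summarised only in subjects still on treatment, but the documents do not support so firm a statement. The ambiguity does not help Week 4.

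**The label is not prescribed.** A subject treated for exactly 6 weeks is also due a 14-day visit, and no text says how coinciding visits are recorded. The omission is therefore implied, not stated. This stands, and it is why the point says that a subject can be affected.

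**Nominal-visit summaries are legitimate** in a small descriptive study with no formal sample size. That is true, but it does not explain leaving an on-time sample without a row.

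**Mapping cannot recover early stoppers.** Someone who stops on Day 12 has no EoT sample near Day 42. This also stands, and the fix needs a second part for such subjects.

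**ECG.** A reader might extend the point to ECGs. The protocol allows the on-treatment tracing "once between days 7 and 21, at EoT and at unscheduled visits, if applicable", while SAP 10.6 says "A 12-lead ECG is collected at Screening, Day 1, Day 10 and EoT". But both schedules place that tracing in the Day 10 column, with a footnote allowing Days 7 to 21. Recorded there, it stays in the Day 10 row whatever its date, so no loss is shown.

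**Conclusion.** The gap is real and worth closing before unblinding. Under the SAP's label rule, an EoT sample drawn on time for Week 4 or Week 6 has no stated route into that week's GMI, beta-D-glucan or PCR summary, and the subject also drops from the target-reduction percentages. This rests on two assumptions: that the sample is recorded as EoT, and that no other sample carries the week's label.

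The size is unknown because the documents give no distribution of EoT days. A reader might infer that a large share of each arm is lost, since 6 weeks is the recommended minimum. That does not follow: treatment may run to 13 weeks. Any count of subjects ending by Day 42 would also mix those whose sample can be placed with those who stopped too early. The direction of any bias is likewise unknown, because subjects stop both for improvement and for failure.

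The consequence is confined to secondary and exploratory biomarker summaries at two weeks.

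**What to change.** Amend SAP 6.4 for GMI, beta-D-glucan and PCR:

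- When no sample carries the Week 4 or Week 6 label, use a scheduled EoT sample whose study day falls in a pre-set window around Day 28 or Day 42. The window could be the ±2-day visit window or a somewhat wider one, fixed before unblinding.
- Show n per arm at each week, with the number of values taken from EoT.
- For subjects who stopped earlier, present a last-available-value summary up to Day 42 beside the observed one, following SAP 8.2.15.
- Reconcile Protocol 15.15 and 15.21 with Protocol Table 5 and SAP Table 2 on whether GMI is taken at the Day 42 contact.

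Leave unscheduled samples in the listings, because they may be prompted by a subject's condition. Leave Days 7 and 14 as they are: wider windows there could take in the separately scheduled Day 5 and Day 10 samples.

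The cost is a paragraph and a short derivation. Study Day is already defined in SAP 6.2, and no new data are needed. The drawbacks are that some values will be a few days off target and that the last-value summary mixes times since baseline, so it should be read beside the observed one and not in its place.
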